## physIQ Alert System – Ileostomy

Patients:

Any positive symptom (dehydration, infection, or obstruction)
≥1200 ml ostomy output over one day
A high risk alert
A predefined number of standard alerts in a day

Table 4: PhysIQ alerts system for CAPE navigator or monitoring nurse for Ileostomy

For ileostomy the thresholds for the high-risk alerts and the number of standard alerts may be changed from patient to patient based on how each case progresses and the density and frequency of alerts. Determining the optimal thresholds for these two types of alerts will be a key aim of this study. The goal is again maximizing signal while minimizing noise.

If any of these conditions listed in Table 4 are met the monitoring nurse will call the patient and go through a predefined note with the following data elements and questions.

Infection Symptom
 
 
a) Fever
 
b) Dysuria
 
c) Redness at ostomy site
 
d) Drainage or swelling at ostomy site
 
e) Other (Free Text)
 

Obstruction Symptom
 
 
a) Nausea
 
b) Vomiting
 
c) Bloating
 
d) Decreased or no ostomy output
 
e) No gas through ostomy
 

Dehydration Symptom
 
 
a) Lightheadedness
 
b) Dry mouth
 
c) Low or dark urine output
 
d) Dizziness
 
e) Increased ostomy output
 

Symptom Change (Obstruction, Dehydration, Infection) [This can show up if any symptom is picked]
 
 
1. New
 
2. Worsening
 
3. Stable
 
4. Improving
 
5. Resolved
 

Ostomy output
 
 
a) 500-1200cc
 
b) >1200cc
 
c) <500cc
 

Is patient NPO? Yes/No

Is patient on antibiotics? Yes/No

Patient is on stool thickening regimen?
 
 
a) None
 
b) Metamucil powder 1 tsp bid
 
c) Imodium 2mg bid w/ meals (20 mins before meals)
 
d) Imodium 2mg qid w/ meals (20 mins before meals)
 
e) Imodium 4mg qid w/ meals (20 mins before meals)
 
f) Stool thickening managed by clinical team
 

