#### **FOLLOWUP PLAN**

1. Case Communication to Clinical RN
2. Case Communication to Ostomy RN
3. Call Clinical RN
4. Call Ostomy RN
5. Consider Call Clinical RN
6. Evaluate trend of ostomy output
7. Stool thickening initiation Metamucil powder 1 tsp bid
8. Stool thickening escalation Imodium 2mg bid w/ meals (20 mins before meals)
9. Stool thickening escalation Imodium 2mg qid w/ meals (20 mins before meals)
10. Stool thickening escalation Imodium 4mg qid w/ meals (20 mins before meals)
11. Stool thickening escalation management by clinical team
12. IV fluids administration
13. Consider IV fluids administration
14. Consider Lab tests BMP, Mag, Phos
15. Consider Lab test CBC
16. Advance Diet as Tolerated (Clear liquids for 6 hours and then advance as tolerated to low residue diet)
17. Continue NPO status
18. Possible urgent clinic evaluation
- 19. Assess for home visit**

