#### **LOGIC:**

- a) MCI, Afib w/ RVR, Tachycardia, Tachypnea (1, 3, 6)
- b) Other physiologic alert (5)
- c) Ostomy output >1200cc and patient on no stool thickening regimen (1, 5, 7, 13)
- d) Ostomy output >1200cc and patient on metamucil stool thickening regimen (1, 5, 13, 8)
- e) Ostomy output >1200cc and patient on imodium 2mg bid stool thickening regimen (1, 5, 13, 9)
- f) Ostomy output >1200cc and patient on imodium 2mg qid stool thickening regimen (1, 5, 13, 10)
- g) Ostomy output >1200cc and patient on imodium 4mg qid stool thickening regimen (1, 3, 13, 11)
- h) Ostomy output <500cc (1, 3)
- i) Has ANY Obstruction symptom, NEW, or WORSENING Obstructive Symptom, Patient not NPO (1, 3, 14)
- j) Has ANY Obstruction symptom, RESOLVED Obstructive Symptom, Patient not NPO (1)
- k) Has ANY Obstruction symptom, NEW or WORSENING Obstructive Symptoms, Patient NPO (1, 3, 14, 17)
- l) Has ANY Obstruction symptom, STABLE or IMPROVING Obstructive Symptoms, Patient NPO (17)
- m) Has ANY Obstruction symptom, RESOLVED Obstructive Symptoms, Patient NPO and Ostomy output 500-1200 (1, 3, 16)
- n) Has ANY Obstruction symptom, RESOLVED Obstructive Symptoms, Patient NPO and Ostomy output >1200, patient not on stool thickening regimen (1, 3, 16)

- o) Has the following Infectious symptoms (Redness at ostomy site, Drainage or swelling at ostomy site), NEW OR WORSENING Infectious Symptoms, Patient not on antibiotics (2, 4, 15)
- p) Has the following Infectious symptoms (Redness at ostomy site, Drainage or swelling at ostomy site), RESOLVED Infectious Symptoms, Patient not on antibiotics (2)
- q) Has the following Infectious symptoms (Redness at ostomy site, Drainage or swelling at ostomy site), NEW OR WORSENING Infectious Symptoms, Patient on antibiotics (2, 4, 15, 18)
- r) Has the following Infectious symptoms (Redness at ostomy site, Drainage or swelling at ostomy site), RESOLVED Infectious Symptoms, Patient on antibiotics (2)
- s) Has the following Infectious symptoms (Fever, Dysuria or Other), NEW, WORSENING, IMPROVING, OR STABLE Infectious Symptoms, Patient not on antibiotics (1, 3, 15)
- t) Has the following Infectious symptoms (Fever, Dysuria or Other), RESOLVED Infectious Symptoms, Patient not on antibiotics (1)
- u) Has the following Infectious symptoms (Fever, Dysuria or Other), NEW OR WORSENING Infectious Symptoms, Patient on antibiotics (1, 3, 15, 18)

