- v) Has the following Infectious symptoms (Fever, Dysuria or Other), RESOLVED Infectious Symptoms, Patient on antibiotics (1)
- w) Has ANY Dehydration symptom, NEW, or WORSENING Dehydration Symptom, Patient not NPO (1, 3, 12, 14)
- x) Has ANY Dehydration symptom, STABLE OR IMPROVING Dehydration Symptom, Patient not NPO (1, 5, 13)
- y) Has ANY Dehydration symptom, RESOLVED Dehydration Symptom, Patient not NPO (1)

Table 5: CAPE Navigator or monitoring nurse alerts system for clinical team for Ileostomy

Table 5 will be configured into a note template within EPIC that allows for data elements to be captured and have all the logics built in to automatically highlight the recommended options for the monitoring nurse. The EHR smart note will be tested out by the research team to ensure the logic is correct.

If patients have any high risk alerts (MCI, Afib with RVR, Tachycardia, Tachypnea), the monitoring nurse will route a note and call clinical RN and evaluate the trend of ostomy output. All other physiological alerts will result in consideration call to clinical RN.

If patient ostomy output  $>1200\text{cc}$  and patient not on stool thickening regimen yet, the monitoring nurse will send note and call clinical RN, consider IV fluids administration and start stool thickening regimen escalation. Monitoring RNs will call clinical RNs for guidance on IV fluid administration guidance. The stool regimen escalation can occur daily while the output is  $\geq 1200\text{ml}$  in 24 hours. There is no monitoring nurse de-escalation protocol, and this will be performed by the clinical team. If a patient is non-adherent to Metamucil and/or Imodium and output is  $\geq 1200\text{ml}$  in 24 hours, medications will be maintained without escalation and patient will be counseled on the importance of adherence to medications. If the output continues to be greater than  $\geq 1200\text{ml}$  in 24 hours and there are no further options for escalation, the monitoring nurse will call the clinical care team for further guidance.

If ostomy output is  $<500\text{cc}$ , monitoring nurse will route note and call clinical RN. If patient has any new or worsening obstruction symptom but **not NPO** yet, monitoring nurse will route note and call clinical RN, and consider lab tests (BMP, Mag, Phos). If the obstructive symptoms resolve while patient is NPO, home health RNs will route note to clinical RN.

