If patient has new or worsening obstruction symptoms but **is NPO already**, monitoring nurse will route note and call clinical RN, consider lab tests (BMP, Mag, Phos), and continue NPO status. If patient obstruction

symptom is stable or improving under the NPO status, monitoring nurse will keep patient NPO. If patient has resolved obstructive symptoms, still NPO and ostomy output is >1200 cc or between 500-1200 cc, monitoring nurse will note and call clinical RN, and instruct patients to advance diet as tolerated.

Any new or worsening redness at ostomy site, drainage or swelling at ostomy site, but **patient not on antibiotics**, monitoring nurse will note and call the ostomy RN for guidance in management, and consider CBC labs. If the above symptoms resolve without antibiotics, home health RN will call ostomy RN to update.

If patient has new or worsening redness at ostomy site, drainage or swelling at ostomy site, and is already on antibiotics, home health RNs will note and call ostomy RN, consider CBC labs and urgent clinic evaluation. If above symptoms resolve with antibiotics, home health RN will call ostomy RN.

Any new, worsening, improved or stable fever, dysuria or other infectious symptoms, but patient **not on antibiotics**, the monitoring nurse will note and call clinical RNs, and consider CBC labs. If the above symptoms resolve without antibiotics, the monitoring nurse will route note to clinical RN.

If patient has any new, worsening, improved or stable fever, dysuria or other infectious symptoms, **but is already on antibiotics**, the monitoring nurse will note and call clinical RNs, and consider CBC labs and urgent clinic visits. If the above symptoms resolve with antibiotics, the monitoring nurse will route note to clinical RN.

If patient has new or worsening dehydration symptoms, but not NPO, monitoring nurse will note and call clinical RN, consider IV fluids administration, and consider labs (BMP, Mag, Phos). If the dehydration symptoms are stable or improving while patient is not NPO, the home health nurses will route note to clinical RN, consider call clinical RN, and consider IV fluids administration under guidance of clinical team. When dehydration symptoms resolve, the home health RNs will route note to clinical RN.

We will be evaluating the high risk alerts and other physiological alerts to find the optimal alert types, thresholds and alerting frequency to maximize signal and minimize noise.

[figure not shown]

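### Table 5 has no row for output above 1200 cc once the clinical team manages stool thickening, so the EPIC note logic omits a call that the narrative requires

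*Protocol*

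**What the plan says.** All of this is in Protocol section 2.2.

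- **Regimen field.** The predefined note offers six options: a none, b Metamucil, c to e three rising Imodium doses, and f, "Stool thickening managed by clinical team".
- **High-output rows.** In the LOGIC list (Table 5), rows c to g each pair output above 1200 cc with one regimen, in the order of options a to e. Row g is "Ostomy output >1200cc and patient on imodium 4mg qid stool thickening regimen (1, 3, 13, 11", that is: note, call the clinical RN, consider IV fluids, and follow-up item 11, "Stool thickening escalation management by clinical team".
- **Row n.** The only other row that uses output above 1200 cc is limited to patients without a regimen: "RESOLVED Obstructive Symptoms, Patient NPO and Ostomy output >1200, patient not on stool thickening regimen (1, 3, 16".
- **Dehydration rows.** Rows w to y apply only to patients who are not NPO. Row w is "Has ANY Dehydration symptom, NEW, or WORSENING Dehydration Symptom, Patient not NPO (1, 3, 12, 14". Row x (stable or improving) gives a note, a consider-call prompt and consider IV fluids. Row y (resolved) gives a note. One of the dehydration symptoms that can be ticked is "Increased ostomy output".
- **Narrative after Table 5.** If output remains at or above 1200 ml in 24 hours and escalation is exhausted, the nurse must call the clinical care team. For resolved obstruction in a patient "still NPO and ostomy output is >1200 cc or between 500-1200 cc, monitoring nurse will note and call clinical RN", and the nurse also tells the patient to advance the diet. No regimen condition is attached.
- **Use of the table.** Table 5 is to be configured as an EPIC note that highlights the nurse's recommended options. Nurse messages are to be forwarded to the colorectal pool according to the protocol and that logic.

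**The concern.** The escalation ladder ends in a state that the table does not recognise. Row g sends the patient to option f. If output is still high the next day and the nurse records f, no output row fires. The narrative requires a call at that point, and the tool meant to prompt the nurse shows none unless another row happens to fire.

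This matters because section 1.2 gives dehydration as the reason ileostomy patients are readmitted, and these patients have already used up the nurse-led thickening steps. Testing the EPIC note against Table 5 would not reveal the omission, since Table 5 is the specification.

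A second mismatch lies next to it. Row n's restriction to patients without a regimen has no counterpart in the narrative it should implement.

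**Working it through.** The plan gives no figure to reproduce, so the check applies the Table 5 rows to the note's fields.

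**Inputs.** Codes from the FOLLOWUP PLAN list: 1 note to clinical RN, 3 call clinical RN, 5 consider call, 11 thickening passes to the clinical team, 13 consider IV fluids, 16 advance diet, 17 continue NPO. Option f is taken as being on a regimen, because option a is the one for none. Coding f as no regimen would fire row c and recommend starting Metamucil, which contradicts the hand-over.

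**Step 1, coverage.** There are 6 regimen options and rows c to g cover 5 of them. 6 − 5 = 1 uncovered, option f.

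**Step 2, field states.** Set output above 1200 cc with no physiologic alert, obstruction symptom or infection symptom. NPO (2 values) × dehydration status (6 values) = 12 states.

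| NPO | Dehydration status | States | Option f now | Option e |
|---|---|---|---|---|
| No | none ticked | 1 | nothing | call |
| No | new, worsening | 2 | call (row w) | call |
| No | stable, improving | 2 | consider call (row x) | call |
| No | resolved | 1 | note only (row y) | call |
| Yes | any of 6 | 6 | nothing | call |

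Totals for f: call 2, consider call 2, note only 1, nothing 1 + 6 = 7; the sum is 12. Option e gets a firm call in 12 of 12 through row g. Options a to d get a note and at least a consider-call prompt in 12 of 12 (rows c to f), with a firm call only in the 2 states where row w fires.

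**Step 3, obstruction status added.** 2 × 6 × 6 = 72 states per option.

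- Option f without a note: not NPO 3 × 1 = 3, NPO 4 × 6 = 24, total 27.
- Option f without a call or consider-call prompt: not NPO 4 × 2 = 8, NPO 4 × 6 = 24, total 32.
- Options a to e: 0 and 0.

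**Step 4, resolved obstruction, NPO, output above 1200 cc** (no alert or infection symptom; dehydration rows cannot fire under NPO). The narrative requires codes 1, 3 and 16.

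| Option | Rows fired | Note | Call | Advance diet |
|---|---|---|---|---|
| a | c, n | yes | yes | yes |
| b, c, d | d, e, f | yes | consider only | no |
| e | g | yes | yes | no |
| f | none | no | no | no |

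An earlier narrative sentence asks for less: "If the obstructive symptoms resolve while patient is NPO, home health RNs will route note to clinical RN". Under f even that note is not highlighted. Row n therefore departs from the narrative for options b to f, not for f alone.

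**Step 5, after adding a row with codes 1 and 3 for option f.** Step 2 becomes a call in 12 of 12. The 27 and 32 in step 3 both become 0. In step 4, f gains the note and the call but still lacks code 16.

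**The case against.** The strongest reply is that the protocol already deals with this state. The narrative call when escalation is exhausted applies most naturally after code 11, because row g itself still lists an escalation step. What is missing is then only an on-screen prompt for a written instruction. This stands, and it is why the point concerns decision support and not the care pathway.

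Other parts of the reply also stand:

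- Table 4 makes the nurse phone the patient at 1200 ml or more.
- In a patient who is not NPO, ticking increased output as a dehydration symptom fires row w or row x unless it is marked resolved.
- Six of the 7 empty states are NPO with no obstruction symptom recorded, although the table's NPO advice appears only in obstruction rows. They are empty partly because rows w to y exclude NPO patients, which is a separate limit.
- Option e is the only regimen whose output row gives a firm call, so 12 of 12 is the most favourable comparator.
- The logic is provisional. The study has 10 patients, and finalising the alerts and the note is one of its outputs.

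The reply does not remove the mismatch. Patients are managed under the table in the meantime. Control of thickening by the clinical team does not by itself tell that team each day's output.

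A reader might infer that patients under option f are left without follow-up, or that 7 in 12 high-output days would go unanswered. The documents support neither. The narrative and the patient call still apply, and the counts weight every field combination equally, whatever its frequency.

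**Conclusion.** The point holds as a minor inconsistency. Table 5 covers 5 of 6 regimen options for output above 1200 cc. It omits the one to which its own last escalation step leads, and so does not encode a call that the narrative requires. Under option f nothing is highlighted in 7 of 12 field states, subject to the NPO caveat above. The number of patient-days affected is unknown and could be zero.

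The conclusion assumes that f counts as being on a regimen and that the nurse records f after code 11. A nurse who went on recording e would still trigger row g, but nothing in the protocol tells the nurse to do so.

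The row n mismatch is a separate finding that affects options b to f. No endpoint, sample size or analysis is touched by either.

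**What to change.** 1. Add a Table 5 row for output above 1200 cc with regimen option f, codes 1 and 3. Add code 13 if the clinical team confirms it. Code 3 carries out the required call, because section 2.2 counts clinical RNs as part of the clinical care team.
2. Add one matching case to the EPIC note test: output above 1200 cc, option f, no symptoms or alerts; expected result, note and call.
3. Reconcile row n with the narrative, as the clinical team confirms. Either drop its regimen condition so that codes 1, 3 and 16 apply under every option, or write the regimen condition into the narrative. The row in item 1 does not settle this, since it leaves out code 16.

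The cost is one added row, one test case, and one edit to row n or to the narrative sentence.

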Figure 2: Process map for Ileostomy Patients

If care is escalated to the clinical care team which includes ostomy RNs, clinical RNs, and Physicians, the care team will pursue various interventions including counseling, altering medication therapy such as antibiotic therapy, procedures such as debridement or drainage, urgent visits to the colorectal surgery clinic ideally within 72 hours, and if no other available options readmission. These workflows will be left

to the discretion of the clinical care team given the nuance in taking care of these high-risk patients and the existing relationship and prior history with these providers. There are some standardized workflows that will be followed by the care team that are of note. Infusions of IV fluids will occur if the patient has  $\geq 1200$  ml of ileostomy output and dehydration symptoms. If these symptoms are identified, the goal will be to have monitoring nurse perform infusion at the patient's home. Also, all messaging from the monitoring nurses will be forwarded to the colorectal/ileostomy pool per protocol and logic in Table 5 to create the most rapid response back to the patient if required.

The final specs of the study will include:

1. Optimal inclusion/exclusion criteria.
2. Specific thresholds for high risk alerts for each use case
3. Specific thresholds for standard alerts (likely use physIQ standard thresholds)
4. Finalized physIQ alerts to CAPE navigators and monitoring nurse
5. Finalized CAPE navigator and monitoring nurse alerts to clinical care team
6. Finalized EPIC note
7. Finalized process maps
8. Finalized workflows by clinical care team
9. Discussion with physIQ to optimize the pinpointIQ portal to best support the CAPE navigators and monitoring nurse

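### Table 5 and the text around it disagree in four places: IV fluids in row w, the 1200 ml cut-point, the call in row c, and an extra condition in row n

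*Protocol*

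**What the plan says.** All of this is in Protocol section 2.2. The follow-up plan numbers the nurse's options. The ones that matter here are 3 (call the clinical RN), 5 (consider calling the clinical RN), 12 (give IV fluids), 13 (consider IV fluids) and 16 (advance diet).

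- **Row w.** Table 5: "Has ANY Dehydration symptom, NEW, or WORSENING Dehydration Symptom, Patient not NPO (1, 3, 12, 14". The narrative after the table: "If patient has new or worsening dehydration symptoms, but not NPO, monitoring nurse will note and call clinical RN, consider IV fluids administration". Later, among the care team's standardized workflows: "Infusions of IV fluids will occur if the patient has" at least 1200 ml of output together with dehydration symptoms.
- **Cut-point.** Table 4 alerts on "≥1200 ml ostomy output over one day". The narrative says "The stool regimen escalation can occur daily while the output is" at or above 1200 ml in 24 hours, and the rule for non-adherent patients uses the same threshold. Rows c to g and row n use a strict >1200, and the note's output bands put 1200 in the 500–1200 band.
- **Row c.** Table 5: "Ostomy output >1200cc and patient on no stool thickening regimen (1, 5, 7, 13". Its narrative: "the monitoring nurse will send note and call clinical RN, consider IV fluids administration and start stool thickening regimen escalation". The next sentence adds: "Monitoring RNs will call clinical RNs for guidance on IV fluid administration guidance".
- **Row n.** For an NPO patient with resolved obstruction and output above 1200, Table 5 prompts code 16 only if the patient is on no stool-thickening regimen. The narrative for rows m and n gives the same action for output of 500–1200 or above 1200, and does not mention the regimen.

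The text after Table 5 says the logic will be configured in an EPIC note template that highlights the recommended options automatically, and that the research team will test it.

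**The concern.** Table 5 and its narrative describe the same nurse actions, and one of them has to be the specification for the EPIC note. Where they differ, the prompt shown for a given patient depends on which text the builder follows. Two of the differences concern treatment: whether to give IV fluids or to consider them, and the output at which stool-thickening prompts begin. A third concerns how firmly the nurse is told to involve the clinical RN.

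Finalizing the alerts, the EPIC note and the workflows is a stated output of the study. If the starting rule is ambiguous, the intervention as delivered cannot be described exactly, and later threshold changes have no clear baseline.

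**Working it through.** The protocol gives no statistical figure on this point, so the check sets the texts side by side.

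**1. Row w and the cut-point, by reported 24-hour output** (non-NPO patient with a new or worsening dehydration symptom)

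| Output | Table 4 output alert | Note band | High-output rows c–g | Row w | Narrative for row w | Care-team infusion workflow |
|---|---|---|---|---|---|---|
| <500 | no | <500 | none | 12: give | consider | silent |
| 500 to <1200 | no | 500–1200 | none | 12: give | consider | silent |
| exactly 1200 | yes | 500–1200 | none | 12: give | consider | infusion occurs |
| >1200 | yes | >1200 | row for the current regimen | 12: give | consider | infusion occurs |

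The row w and narrative columns disagree on every line. This is not loose labelling. Codes 12 and 13 are separate options, rows c to g and x use 13, and row w is the only row that uses 12. The narrative for row x (stable or improving symptoms) says to consider fluids, which matches its code 13, so within the dehydration rows the mismatch is specific to row w.

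The exactly-1200 line shows the cut-point problem. Table 4 alerts, the escalation rule permits a step up, and the infusion workflow applies. The note, however, files the value in the middle band and none of rows c to g fires. The narrative is itself mixed: the high-output paragraph opens with >1200 and then uses ≥1200.

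**2. Row c.** The table gives code 5 (consider calling). The narrative for the same patient, output above 1200 and not yet on a regimen, says to call, which is code 3.

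**3. Row n.** The note lists six regimen entries, one of which is none, leaving 6 − 1 = 5 regimens. For a patient on any of those five, NPO, with resolved obstruction and output above 1200, the narrative says to call and advance the diet, but row n does not fire.

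This interacts with the cut-point. Suppose row m becomes 500 to <1200 and row n becomes ≥1200 with its extra condition kept. A patient on a regimen at exactly 1200 ml would then leave row m without entering row n, and would lose a prompt that row m gives now.

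**The case against.** The strongest defence is that little follows in practice. Highlighted options are recommendations. Row w carries code 3, so the clinical RN is called whichever IV wording applies. At exactly 1200 ml the Table 4 alert still fires, the nurse still phones the patient and escalation is still permitted; only the automatic highlight is lost. The note is to be tested, and the thresholds are meant to evolve. This limits the weight of the point and is accepted. It does not remove the point, because testing needs one reference rule: a tester working from Table 5 would pass row w, and one working from the narrative would fail it.

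Three stronger readings are tempting, and the protocol does not support them.

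- A reader might infer that row w contradicts the infusion workflow below 1200 ml. That workflow says when infusion will occur, not that it occurs only then. It describes the care team after escalation, with other care left to that team's discretion. Below 1200 ml it is silent, so the direct conflict is between row w and its own narrative.
- A reader might infer that rows d to f are also wrong to use code 5. The instruction to call covers only patients not yet on a regimen, which is row c. The sentence about calling for IV-fluid guidance fits codes 5 and 13: a nurse who is considering fluids calls.
- A reader might infer a defect because the text states no precedence when several rows fire together. If call and consider calling are both highlighted, the nurse can simply call. Figure 2, the process map, is not available here, so what it shows cannot be checked.

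**Conclusion.** The point holds as four mismatches in wording: row w's code 12 against its narrative; ≥1200 against >1200; row c's code 5 against its narrative; and row n's extra condition.

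Its size is modest. The cut-point difference affects only a recorded value of exactly 1200 ml. That value may be less rare than it sounds, because volumes are patient-reported and may be rounded, but rounding is an assumption. The protocol does not say how many of the 10 patients would reach any of these situations, and no estimate is offered. Counting combinations of note fields would not measure it either, since row w does not depend on regimen and the same single code would be counted repeatedly. No endpoint, sample size or error rate is affected.

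The corrections should still be made. They concern a treatment prompt and a decision threshold that are about to be programmed, and they cost little. The conclusion rests on the current text alone and does not presume which version the clinicians intended.

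**What to change.** With clinical sign-off, and before the EPIC note is built:

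1. **Row w:** change code 12 to 13. If the clinicians do intend a prompt to give fluids, keep 12 and amend the narrative.
2. **Cut-point:** use ≥1200 ml throughout: note bands of 500 to <1200 and ≥1200, rows c to g, rows m and n, and the matching narrative sentences.
3. **Row c:** change code 5 to 3, or amend its narrative to say consider calling.
4. **Row n:** remove the stool-thickening condition. Do this together with item 2, for the reason shown in the working.

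A new row prompting definite infusion at ≥1200 ml with any unresolved dehydration symptom is not advised. It would extend that prompt to stable or improving patients, for whom row x and its narrative both say consider. Nor should increased ostomy output be removed from the dehydration symptoms for this purpose; nothing in the protocol makes that exclusion.

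The cost is protocol and note-template wording. No procedure, visit or data item is added.

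### Table 5 has no dehydration rule for NPO patients, so at 500-1200cc new or worsening dehydration can prompt nothing beyond continuing NPO

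*Protocol*

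**What the plan says.** Protocol section 2.2 sets out a predefined note, a numbered list of follow-up actions, and the Table 5 logic that links them. The logic is to be built into the EPIC note so that recommended actions are highlighted automatically.

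- **Dehydration, new or worsening (row w):** "Has ANY Dehydration symptom, NEW, or WORSENING Dehydration Symptom, Patient not NPO (1, 3, 12, 14". The numbers are action codes: 1 note to the clinical RN, 3 call the clinical RN, 12 IV fluids, 14 consider labs.
- **Dehydration, stable or improving (row x):** "Has ANY Dehydration symptom, STABLE OR IMPROVING Dehydration Symptom, Patient not NPO (1, 5, 13". Code 5 is consider a call; code 13 is "Consider IV fluids administration".
- **Dehydration, resolved (row y):** code 1, again only when not NPO.
- **Obstruction in NPO patients:** row k, "Has ANY Obstruction symptom, NEW or WORSENING Obstructive Symptoms, Patient NPO (1, 3, 14, 17", and row l, "Has ANY Obstruction symptom, STABLE or IMPROVING Obstructive Symptoms, Patient NPO (17". Code 17 is to continue NPO. Rows m and n cover resolved obstruction in NPO patients.
- **The note itself:** NPO is its own item, "Is patient NPO? Yes/No". Symptom change is listed once for all three symptom groups with the remark "This can show up if any symptom is picked".
- **Narrative after Table 5:** "If patient has new or worsening dehydration symptoms, but not NPO, monitoring nurse will note and call clinical RN, consider IV fluids administration". The sentence on stable or improving dehydration carries the same restriction. The sentence on resolved dehydration does not.

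**The concern.** The obstruction rows are written for both NPO states, but the dehydration rows are written for one. A patient with no oral intake therefore gets a weaker prompt than a patient who is not NPO and has the same symptoms. Section 1.2 names dehydration as the reason ileostomy patients are readmitted, and avoiding readmission is the purpose of the alert pathway.

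This is a stated rule that gives the worse answer when it is followed; it is not a detail left for later. It bears on patient safety and on the content of the intervention being tested. It does not touch sample size or analysis.

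**Working it through.** The protocol gives no figure to reproduce, so the check is one of rule coverage.

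**Setting.** NPO patient, output 500-1200cc, dehydration new or worsening, no infection symptom, no physiologic alert.

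**Which rows can fire.** Rows a-b need a physiologic alert. Rows c-g need more than 1200cc. Row h needs less than 500cc. Rows i-j and w-y need a patient who is not NPO. Row n needs more than 1200cc. Rows o-v need an infection symptom. Only k, l and m remain, and all three depend on obstruction.

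| Obstruction status | NPO | Not NPO |
|---|---|---|
| None | no code | 1, 3, 12, 14 |
| Stable or improving | 17 (row l) | 1, 3, 12, 14 |
| New or worsening | 1, 3, 14, 17 (row k) | 1, 3, 12, 14 |
| Resolved | 1, 3, 16 (row m) | 1, 3, 12, 14 |

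Code 16 is to advance the diet. A combination is called unprompted if it highlights no note, call, consider-call or fluids code, that is none of 1, 2, 3, 4, 5, 12, 13.

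**Reading A: symptom change recorded separately for each symptom group.**
- All combinations: 2 dehydration values × 6 stool regimens × 6 obstruction states (none plus five change values) = 72.
- Unprompted: 2 × 6 × 3 (none, stable, improving) = 36. Of these, 2 × 6 × 2 = 24 show only code 17 and 2 × 6 × 1 = 12 show no code.
- Regimen changes nothing in this band. Without it, 2 × 6 = 12 distinct states, of which 6 are unprompted (4 with code 17 only, 2 with no code).

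**Reading B: one shared change field.** New or worsening then applies to any obstruction symptom too, so row k fires whenever one is present.
- All combinations: 2 × 6 × 2 (obstruction yes or no) = 24.
- Unprompted: 2 × 6 × 1 = 12, all with no code. Without regimen, 2 of 4.

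**Comparison with patients not NPO.** Unprompted: 0 of 72 and 0 of 24. A fluids code (12 or 13) is highlighted in 72 of 72 and 24 of 24. For NPO patients it is highlighted in 0 of 72 and 0 of 24.

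**Stable or improving dehydration, NPO, same band.** Reading A: 36 of 72 unprompted. Reading B: 24 of 24 (12 with code 17 only, 12 with no code).

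**Wider check.** All rows a-y were coded under Reading A and run over every NPO combination of alert (3), output band (3), regimen (6), obstruction (6), two infection groups (6 × 6) and antibiotics (2): 3 × 3 × 6 × 6 × 6 × 6 × 2 = 23,328. Dehydration status changes the highlighted output in 0 of them.

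**Outside the band.** Below 500cc, row h gives a note and a call. Above 1200cc, rows c-g and the narrative largely cover the patient. No gap is claimed in either band.

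**The case against.** **The state may be rare.** No action code starts NPO, and resolution of obstruction at 500-1200cc triggers row m, which alerts the clinical RN and advances the diet. An NPO patient with no obstruction symptom must have been made or kept NPO for a reason the protocol does not describe. The band also excludes any alert or infection symptom, and the cohort is 10 patients. All of this stands as a limit on frequency. It does not supply a rule, and the note records NPO independently of obstruction.

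**The stable or improving obstruction case depends on the form.** With one shared change field, row k fires and gives a note, a call and labs. This stands. Row k still offers no fluids code, and the gap with no obstruction symptom remains under both readings.

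**The regimen multiplier inflates 36 of 72.** Fair; 6 of 12 and 2 of 4 are the figures to use.

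**There are backstops.** Any positive symptom makes the nurse phone the patient under Table 4. Question 2 asks twice daily about being unable to eat or drink. Question 7 sends patients with no urine for 12 hours, or who pass out, to a clinician or the emergency room. A tachycardia alert fires row a. The highlighted actions are recommendations, so a nurse may do more. These reduce the risk, but none prompts the nurse to tell the clinical RN about the dehydration. Care-team discretion in section 2.2 begins only once care has been escalated, and the infusion workflow there also needs output of at least 1200 ml.

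**The note will be tested and finalised.** Testing it against Table 5 would reproduce the gap, because the table and the narrative share it.

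**The restriction may be deliberate,** leaving hydration of NPO patients to the clinical team. That is possible, but no rationale is given, and the clinical team would still need to be told. The Figure 2 process map is not shown and could not be checked.

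**Conclusion.** The concern holds. All three dehydration rows and both narrative sentences on active dehydration exclude NPO patients, and no other text shown supplies the missing rule. In the band examined, 6 of 12 distinct states (separate change fields) or 2 of 4 (one shared field) prompt no note, call or fluids, against none for patients not NPO. No NPO state in this band highlights fluids under either reading.

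This rests on the Table 5 wording as printed, on no infection symptom or physiologic alert being present, and on output of 500-1200cc. The counts weight rule states equally and say nothing about how many patients would be affected, which the protocol does not give. The point should be fixed because the rule concerns safety and the correction is small.

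**What to change.** 1. Add three Table 5 rows for NPO patients: new or worsening dehydration, codes 1, 3, 13, 14; stable or improving, codes 1, 5, 13; resolved, code 1.
2. Align the two narrative sentences on active dehydration and the EPIC logic. The resolved row also brings the table into line with the narrative, which has no NPO limit there.
3. Use code 13, with the clinical team confirming the fluid action for NPO patients. Do not simply delete the NPO condition from row w: that would extend code 12 to NPO patients, although the narrative for the same row only asks the nurse to consider fluids. Settle 12 versus 13 in row w at the same time.
4. State whether symptom change is recorded once or for each symptom group.
5. Include every NPO combination in the planned test of the note.

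With the three rows added, unprompted combinations in this band fall to 0 under both readings. The cost is three rows, two sentences and the matching EPIC logic, plus a few more calls to the clinical RN and some extra consider-fluids and lab prompts for NPO patients.
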